**Table 8-7 Overview of Effectiveness Analysis**

Outcome	Primary/Secondary	Statistical Method 1	Statistical Method 2	Statistical Method 3
Annual HV	Primary	MMRM, 95% CI	MMRM + IPTW, 95% CI	Descriptive stats
Height standard deviation score (SDS) and change in height SDS	Primary	MMRM, 95% CI	MMRM + IPTW, 95% CI	Descriptive stats
HVSDS	Primary	MMRM, 95% CI	MMRM + IPTW, 95% CI	Descriptive stats
Change in annual BMI	Primary	MMRM, 95% CI	MMRM + IPTW, 95% CI	Descriptive stats
Change in annual BMI SDS	Primary	MMRM, 95% CI	MMRM + IPTW, 95% CI	Descriptive stats
Change in Bone age	Primary	MMRM, 95% CI	MMRM + IPTW, 95% CI	Descriptive stats
Change in IGF	Primary	MMRM, 95% CI	MMRM + IPTW, 95% CI	Descriptive stats
Change in IGF-I SDS	Primary	MMRM, 95% CI	MMRM + IPTW, 95% CI	Descriptive stats

090177e1a57a0182\Approved\Approved On: 16-Feb-2026 13:43 (GMT)

[1] Continuous variables will be summarized using descriptive statistics which will include the number of patients with data to be summarized (n), mean, standard deviation (SD), median, first and third quartiles (Q1, Q3), minimum, maximum, and the number of missing observations. Descriptive statistics for categorical/qualitative variables will be presented with number of patients (count) and percentage and this will be presented in the format 'n (%)'.

**Analysis of the Secondary Endpoints:**

For secondary endpoints, safety events of interest, medication errors and efficacy measurements, descriptive statistics, counts and proportions, crude incidence rates (i.e., number of events per person years) with associated two-sided 95% confidence intervals will be calculated. Incidence rate is calculated as the number of individual events observed during the time at risk (exposure time), divided by the total number of patient-years at risk for the event, multiplied by 100.

**Table 8-7 Overview of Safety Analysis**

Outcome	Primary/Secondary	Statistical Method [1]	Statistical Method 2
SAEs	Secondary	Descriptive stats	IR, IRR, HR
Non-SAEs	Secondary	Descriptive stats	
Medication Errors	Secondary	Descriptive stats	IR, IRR, HR
Laboratory results	Secondary	Descriptive stats	

[1] Continuous variables will be summarized using descriptive statistics which will include the number of patients with data to be summarized (n), mean, standard deviation (SD), median, first and third quartiles (Q1, Q3), minimum, maximum, and the number of missing observations. Descriptive statistics for categorical/qualitative variables will be presented with number of patients (count) and percentage and this will be presented in the format 'n (%)'.

**Repeated Measures**

This model will only be performed with those patients without treatment switch until a given time point. Continuous variables will be analyzed by a Mixed Model for Repeated Measures (MMRM) under the MAR framework, including all post baseline timepoints data as outcome variables and baseline data as a covariate including the relevant patient/disease characteristics. Repeated time variable will be modeled as a continuous variable and treatment (Genotropin versus Ngenla) as a class variable with an unstructured covariance and least square means along with 95% CI will be presented.

The adjusted mean changes from Baseline at Month 6, 12, 18, 24, etc., for each treatment group will be estimated in the framework of this model, as well as the between group differences and the 95% CIs for the adjusted mean, when applicable.

The MMRM model will be implemented using SAS® (version 9.4 or higher) generalized linear mixed procedure (PROC MIXED) with an unstructured correlation matrix to model the within-patient errors. If this model does not converge, a heterogeneous Toeplitz covariance structure followed by the

090177e1a57a0182\Approved\Approved On: 16-Feb-2026 13:43 (GMT)

heterogeneous first-order autoregressive covariance structure will be considered. Parameters will be estimated using the Newton-Raphson algorithm. Denominator degrees of freedom will be estimated using the Kenward-Roger approximation.

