### 8.2. Setting

The source population for this study will be the subset of patients contributing data to the GloBE-Reg registry who are treated with either long acting Ngenla (somatrogon) or daily hGH Genotropin (somatropin) at the discretion of the prescribing physician. This population is thought to be a representative sample of children treated with Ngenla (somatrogon) and Genotropin (somatropin) across the world. Data will be included from eligible participants of any age who meet the study criteria and who receive care at centers enrolled in GloBE-Reg that have agreed to share their data with Pfizer during the data collection period. The registry is growing and additional centers around the world are expected to be included over the course of the study period.

The data collection period is from September 30, 2025 to August 31, 2035. No sampling will be performed. Participants can be located anywhere in the world and will be followed up to 10 years until the end of the study or one of the following occurs: withdrawal of consent, discontinuation of

either Ngenla (somatrogon) or Genotropin (somatropin), discontinuation from the GloBE-Reg registry, lost to follow up or death.

The treating physician will follow patients treated with Genotropin (somatropin) or Ngenla (somatrogon) as per routine clinical practice and will collect and enter relevant patient data as part of the defined minimum data set collected by the GloBE-Reg registry.

During the study, duration of treatment exposed will be defined as:

Genotropin/Ngenla: (last dose date – baseline date + 1)/365.25,

where baseline date is the initial visit date on the Reported Outcomes eCRF form.

The data collected via GloBE-Reg will be de-identified and sent to Pfizer for analysis. Pfizer will analyze the data to evaluate treatment effectiveness, safety, adherence and compliance.

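### The last covariance fallback, heterogeneous AR(1), is paired only with model-based Kenward-Roger inference, so the 95% CIs of the primary Ngenla-Genotropin differences can be miscalibrated if it is used

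*Protocol*

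**What the plan says.** All of this is in protocol section 8.7, under Repeated Measures.

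- **First choice of covariance:** the model is fitted "with an unstructured correlation matrix to model the within-patient errors".
- **Fallbacks:** "If this model does not converge, a heterogeneous Toeplitz covariance structure followed by the" "heterogeneous first-order autoregressive covariance structure will be considered".
- **Inference:** "Denominator degrees of freedom will be estimated using the Kenward-Roger approximation". No empirical or sandwich variance is named at any step.
- **Mean model:** "Repeated time variable will be modeled as a continuous variable", with treatment as a class variable. The text does not say whether a treatment-by-time term is included.
- **Estimates:** "The adjusted mean changes from Baseline at Month 6, 12, 18, 24, etc., for each treatment group will be estimated", with between-group differences and 95% CIs.

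Section 8.2 sets the length of follow-up: "Participants can be located anywhere in the world and will be followed up to 10 years until the end of the study". The effectiveness overview in Table 8-7 applies this model to every primary outcome. The Longitudinal Model/Sensitivity Analysis applies it again with weights.

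**The concern.** Heterogeneous AR(1) makes the correlation between two visits fall geometrically with the number of visits between them. A child who grows persistently faster or slower than others keeps some correlation between distant visits. AR(1) would then treat those visits as nearly independent and overstate the information each child supplies.

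Kenward-Roger adjusts the degrees of freedom and the small-sample variance on the assumption that the covariance form is right. It does not correct a wrong form. Because time is continuous, each visit-specific difference borrows from the other visits and so depends on the working covariance.

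At stake is the calibration of the 95% CIs for the primary comparisons, in any outcome or subgroup whose model ends at the last step. Interval widths could also differ between outcomes only because different structures converged.

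**Working it through.** The plan states no figure to reproduce. The check asks how far a model-based CI can be off if AR(1) is reached.

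**1. Can the fallback be reached?** Six-monthly estimates over 10 years give at most 20 visits. Covariance parameters for T visits are T(T+1)/2 for unstructured, 2T-1 for heterogeneous Toeplitz and T+1 for heterogeneous AR(1).

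| Years | T | Unstructured | Toeplitz | AR(1) |
|---|---|---|---|---|
| 2 | 4 | 10 | 7 | 5 |
| 5 | 10 | 55 | 19 | 11 |
| 10 | 20 | 210 | 39 | 21 |

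Failure of the unstructured model is plausible with sparse late visits. Failure of Toeplitz as well is possible but less likely.

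**2. Inputs.** Group sizes of 2000 and 700 are from section 8.5, so 700/2700 = 26% are on Ngenla. The within-child correlation is not in the protocol and is assumed constant at 0.3, 0.5 or 0.7. Follow-up is either complete or spread evenly over last visits, unrelated to outcome. The mean model has linear time, with treatment as a main effect or with treatment-by-time.

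**3. Method.** Find the AR(1) parameters that the likelihood converges to under the assumed truth. Compute r = model-based SE / true (sandwich) SE of the drug difference. Coverage of a nominal 95% CI is then 2Φ(1.96 r) - 1.

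**4. Example.** With a true correlation of 0.70 and 10 visits, AR(1) fits a lag-one correlation of 0.70. It therefore implies 0.70^9 = 0.04 between months 6 and 60, where the truth is 0.70.

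**5. Results with constant correlation 0.5, main-effect model.**

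| Visits | r (complete to even drop-out) | Coverage |
|---|---|---|
| 4 | 0.89 to 0.94 | 92% to 93% |
| 10 | 0.67 to 0.77 | 2Φ(1.31) - 1 = 81% to 2Φ(1.51) - 1 = 87% |
| 20 | 0.51 to 0.60 | 2Φ(1.00) - 1 = 68% to 2Φ(1.18) - 1 = 76% |

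Adding treatment-by-time changes little at the worst month, which falls in mid-follow-up: about 82-87% at 10 visits and 68-76% at 20. Over correlations 0.3 to 0.7 and both mean models, the calculated extremes are 91.7-93.9% at 4 visits, 81.1-89.1% at 10 and 68.1-80.8% at 20. Allowing a small margin for other drop-out patterns, these are quoted as about 92-94%, 81-90% and 68-82%.

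**6. The error depends on the time point.** Constant correlation 0.7, 10 visits, treatment-by-time, complete follow-up: coverage is 92.5% at month 12, 84.5% at month 30 and 95.0% at month 60.

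**7. Other assumed truths at 10 visits, treatment-by-time, complete follow-up.**

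- True AR(1) with correlation 0.8: 95.0% throughout.
- Shared level plus decaying part plus noise: 93.3%, 88.1% and 95.0% at months 12, 30 and 60.
- Random intercept and slope: 96.9%, 91.6% and 90.0%. With a treatment main effect only, random slopes instead make the CI conservative: 1-3% of intervals miss, against the nominal 5%.

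**8. Toeplitz** (6 visits, 10% drop-out per visit): 95.0% in the three stationary scenarios and 93.3-95.6% with random slopes.

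**The case against.** The case against is substantial, and much of it limits the point.

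- **Toeplitz comes first.** A reader might infer that failure of the unstructured model leads straight to AR(1). The protocol does not say that. Heterogeneous Toeplitz precedes it, contains the constant-correlation case, and kept coverage near nominal. This stands.
- **The correlation is assumed.** A reader might infer that AR(1) necessarily gives wrong intervals. The protocol gives no correlation, and under a true AR(1) the intervals are right. Adjustment for baseline and patient characteristics would absorb some of the stable difference between children, and the calculation omits those covariates. This stands.
- **Twenty visits is a ceiling.** Follow-up ends at discontinuation, switchers leave this model, and many participants will enter late. This stands. At 4 visits the loss is small.
- **The study tests no hypothesis.** It is tempting to report a false-positive rate of 24-32% at 20 visits. Section 8.5 disclaims a priori testing, so coverage is the right measure. The point survives in that form, because the primary objective includes a comparison and the 95% CI is its stated uncertainty.
- **This belongs in the SAP.** The SAP was not available and may add a robust variance. But section 8.7 itself fixes the fallback order, continuous time and Kenward-Roger, so the pairing is a stated rule and not an omission.
- **Sandwich errors are weak with few patients.** This is true, and the fix has to allow for it.

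**Conclusion.** The point holds conditionally. An ordered fallback list is good practice. The weakness is that its last step carries model-based inference only. If both the unstructured and the Toeplitz models fail, and within-child correlation stays roughly constant at 0.3 to 0.7, coverage at the worst time point is about 92-94% at 4 visits, 81-90% at 10 and at most 20 visits bring it to 68-82%. With categorical time and the constant or mixed correlations examined, coverage stays at 95-96%, so the planned continuous time is part of the cause. With random slopes the direction depends on the mean model and the time point. The documents do not support saying that the primary CIs will be wrong, or that they will always be too narrow.

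**What to change.** Add to section 8.7, after the fallback sequence:

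> If the heterogeneous AR(1) structure is used (and, for consistency, any structured fallback), standard errors and 95% CIs will be based on the empirical (sandwich) variance clustered on patient, with a small-sample bias correction where the number of patients is small (e.g. subgroups), and the structure used will be reported for each outcome.

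The change is needed mainly at the AR(1) step. Including Toeplitz is for consistency, since little error was found there. With the sandwich variance, large-sample coverage is 95% in every scenario above by construction. It corrects interval width only.

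The cost is one sentence and a variance option in the software. Kenward-Roger is given up in fallback models. That loss is negligible at about 2700 patients but leaves somewhat less small-sample protection in small subgroups, which is why the bias correction is included.

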### **Count outcomes or Incidence Rate Ratio**

Poisson regression (or negative binomial regression if data presents overdispersion) will be used to estimate the incidence rate ratio (IRR) along with 95% Wald CI between Ngenla-treated patients and Genotropin-treated patients.

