The sub-optimal adherence with daily hGH is well established, as is the burden of daily injections for both participants and caregivers. Long-acting hGH may obviate the need for the majority of injections currently required in daily hGH products. As demonstrated in animal models and clinical studies, Ngenla may be injected once per week resulting in similar clinical efficacy as daily injections of hGH. In the pivotal global Phase III clinical trial, the primary objective of non-inferiority (clinical comparability) for weekly Ngenla compared to daily hGH was met (annualized height velocity (HV) at Month 12 for once-weekly Ngenla was 10.10 cm/year versus 9.78 cm/year for daily hGH). Low numbers of serious adverse events (SAEs) were reported in both the weekly Ngenla and daily hGH groups, and the majority of adverse events (AEs) were of mild to moderate severity. Thus, weekly Ngenla administration was generally well-tolerated in pediatric participants.

The purpose of the Pfizer Registry of Outcomes in Growth hormone REsearch (PROGRES) 2.0 study will be to address the identified need for long-term effectiveness and safety data on the use of Ngenla (somatrogon) and Genotropin to reflect outcomes that occur in real-world clinical practice.

This noninterventional study is designated as a PASS and is conducted voluntarily by Pfizer.

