#### 8.4. Data Sources

The study will obtain existing data collected in the GloBE-Reg registry. GloBE-Reg is an international, non-interventional registry of bone and endocrine agents, conducted by the project team based at the Office for Rare Conditions at the University of Glasgow, Glasgow, Scotland, United Kingdom. GloBE-Reg is approved by the National Research Ethics Service and Information Governance Authority in the UK.

The registry collects real-world data on both efficacy and safety and allows for sub-studies that can be of interest to any of its stakeholders. The GloBE-Reg steering committee identified an expert working group to develop a minimum data set for the registry. The minimum data set comprises items agreed upon by the expert working group and deemed by consensus to be easily measured in a routine clinical setting across the world to monitor the safety and effectiveness of hGH, both daily and long acting, in children with GHD. To date, GloBE-Reg has collected de-identified, patient-level data from an international cohort of over 3500 participants from across 32 centers in 20 countries. The collected data is comprised of demographics, clinical characteristics, birth and medical history, diagnosis of growth hormone deficiency, therapy, including prior and current GH treatment, concomitant medications, laboratory results, clinician reported outcomes and adverse events.

The registry is a web-based interface linked to a secure database at the University of Glasgow, which is managed and reviewed by the university Central IT Services in compliance with the UK Data Protection Act (2018) and General Data Protection Regulation (GDPR 2016/679). Reporters are healthcare professionals at medical institutions around the world who apply for clinical contributor role-based access accounts for their center. Once access to the registry is obtained, clinicians obtain local approvals to enroll eligible participants at their center, obtain and store each participant informed consent form and can then add routinely collected clinical information. All data are pseudonymized and when the core mandatory modules are entered into the registry and saved, a registry ID is provided. This unique patient identifier is used across all visits, enabling longitudinal follow-up of patients.

Data can also be uploaded using bulk transfer method available in the registry, after the above requirements are met.

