## 8.5. Study Size

The study is descriptive in nature without any *a priori* hypothesis testing; therefore, a formal sample size estimate is not required. All eligible participants treated will be included. It is expected that at least 2000 Genotropin (somatropin) treated and 700 Ngenla (somatrogon) treated participants will be included in the final analysis.

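### The only interval given for the between-drug incidence rate ratio is a Wald interval, which cannot be computed when either drug has no events

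*Protocol*

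**What the plan says.** Section 8.7, under the heading on count outcomes, sets the between-drug comparison as "Poisson regression (or negative binomial regression if data presents overdispersion") and states that this model "will be used to estimate the incidence rate ratio (IRR) along with 95% Wald CI". It names no other interval and no rule for zero or sparse counts.

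The safety overview table in the same section assigns an incidence rate ratio to two rows only, serious adverse events and medication errors. Non-serious events and laboratory results get descriptive statistics. The text on secondary endpoints defines the rate through the "number of individual events observed during the time at risk (exposure time"), so repeat events in one patient count. It also asks for a crude rate with a two-sided 95% interval, without naming the method.

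Section 8.5 expects "at least 2000 Genotropin (somatropin) treated and 700 Ngenla (somatrogon) treated participants". Section 8.2 says that participants "will be followed up to 10 years until the end of the study". No mean follow-up and no event rate appear anywhere. Section 6 says only that "Low numbers of serious adverse events (SAEs) were reported in both the weekly Ngenla and daily hGH groups", referring to the pivotal trial.

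**The concern.** The standard error of a log rate ratio contains one over the event count in each group. With no events on one drug the estimate runs off to zero or infinity, and the Wald interval is undefined or meaninglessly wide. The protocol therefore names a method that fails in a foreseeable situation.

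Ngenla is the smaller group, and the events collected in section 8.3 include leukaemia, pancreatitis, anaphylaxis and intracranial hypertension. A comparison of no events with a few events still says something about how large the ratio could be, and the stated method cannot express it. If the alternative is chosen only after the zero has been seen, the interval for the events of most safety interest becomes a post hoc choice.

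**Working it through.** The protocol states no figure that could be reproduced, so the check rests on its group sizes and on labelled assumptions.

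**Inputs.** From section 8.5: 700 Ngenla and 2,000 Genotropin participants. From the Abstract (study size): 157 Ngenla participants at 30 June 2025. Assumed: mean treated time of 3 years (range 2 to 4), and event rates of 0.5 and 1 per 1,000 patient-years (PY).

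**1. Failure of the interval.** The Wald interval is log(IRR) ± 1.96 × √(1/a + 1/b), where a and b are the event counts. At a = 0 the term 1/a is infinite. A Poisson fit to 0 against 8 events did not settle: log IRR −21.3, standard error about 15,575.

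**2. Chance of no Ngenla event.** P(0) = exp(−rate × PY).

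| Ngenla PY | 0.5 per 1,000 PY | 1 per 1,000 PY |
|---|---|---|
| 700 × 2 = 1,400 | exp(−0.70) = 0.50 | exp(−1.40) = 0.25 |
| 700 × 3 = 2,100 | exp(−1.05) = 0.35 | exp(−2.10) = 0.12 |
| 700 × 4 = 2,800 | exp(−1.40) = 0.25 | exp(−2.80) = 0.06 |

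The range is 6% to 50%. A zero on Genotropin is less likely: at 2,000 × 3 = 6,000 PY and 0.5 per 1,000 it is exp(−3.0) = 0.05. For an early cut at the June 2025 size with an assumed 1.5 years each, 157 × 1.5 ≈ 235 PY, and at 1 per 1,000 P(0) = exp(−0.235) = 0.79.

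**3. Where it does not matter.** At 0.5 per 100 PY, as might hold for pooled serious adverse events, 2,800 PY gives exp(−14), below 0.001.

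**4. What an exact interval gives.** Conditional on the total, the Ngenla count is binomial. Take 0 events in 2,100 PY against 6 in 6,000 PY.

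- Clopper-Pearson: p = 1 − 0.025^(1/6) = 0.459. Upper limit = 0.459/0.541 × 6,000/2,100 = 2.43.
- Mid-P: p = 1 − 0.05^(1/6) = 0.393. Upper limit = 0.393/0.607 × 6,000/2,100 = 1.85.
- Rate difference: 0 − 0.10 = −0.10 per 100 PY.

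For 0 in 2,800 PY against 3, 5, 8, 10 or 20 events in 8,000 PY, the Clopper-Pearson upper limits are 6.91, 3.12, 1.67, 1.27 and 0.58.

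**5. Very few events.** For 1 in 2,800 PY against 3 in 8,000 PY, Wald gives 0.10 to 9.16 and the exact method 0.02 to 11.86. Wald exists here, but the two already differ.

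**6. Does missed overdispersion make rare-event intervals too narrow?** Coverage was simulated at a true ratio of 1, with 700 against 2,000 patients over 4 years and gamma frailty between patients (variance 5, 20 and 50). The planned rule was applied with a one-sided 5% score test, which is an assumption because the protocol names no criterion. At 0.05 to 0.25 per 100 PY, overdispersion was missed in up to 97% of runs, yet coverage in those runs was 0.966 to 0.977. Over all scenarios up to 2 per 100 PY the planned rule covered 0.94 to 0.98, and a patient-level robust variance 0.93 to 0.98.

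**The case against.** Several objections carry weight.

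- The safety table lists the ratio for serious adverse events and medication errors as two rows, not by event type. Pooled serious adverse events will almost surely occur on both drugs at the final size. This stands, and it confines the problem to medication errors, to ratios by type if they are produced, and to early cuts.
- No interim report is scheduled in the milestones. Six-monthly transfers (section 8.6) and annual investigator meetings (section 11) make early summaries possible but not certain. The 79% figure applies only there.
- A zero would not go unreported, because each drug still gets a crude rate with a 95% interval. True, but two separate intervals do not replace the comparison that the protocol announces.
- Sparse-data handling commonly sits in the SAP, which section 8.7 allows to modify the plan, and the analysis is secondary and descriptive. This lowers the importance. It does not remove the point, because the protocol itself names the interval that fails.

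A reader might go further and infer that overdispersion can be missed when events are rare, leaving the Poisson interval too narrow. The documents do not support that. The plan already provides for a switch ("or negative binomial regression if data presents overdispersion"), and where counts are too sparse to trigger it, coverage was above 95%. Under-coverage with repeated events at 3 to 5 per 100 PY (82% to 93% in simulation) arises only if Poisson is kept regardless, for example under a deviance-based check that the protocol does not specify. A score test or the Pearson statistic flagged every one of those data sets, and switching gave 94% to 96%.

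Strong centre effects combined with uneven drug use by centre can reduce coverage for more frequent events. That is a different mechanism and no part of this point.

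**Conclusion.** The point holds in a limited form and is minor. The protocol ties the between-drug ratio to a Wald interval that is not estimable when either drug has no events, and it gives no alternative. The 6% to 50% chance of a zero on Ngenla rests on assumed rates of 0.5 to 1 per 1,000 PY and an assumed 2 to 4 years of mean treated time. At higher rates it fades quickly, and for pooled serious adverse events at the final size it can be disregarded. The failure at zero is arithmetic and depends on no assumption about clustering or about the overdispersion test. There is no case here for replacing the negative binomial switch with a robust variance.

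**What to change.** Keep the Poisson/negative binomial rule in section 8.7. Add one sentence, carried into the SAP: when either drug has zero or very few events, with the cut-off count stated in advance, the rate ratio is reported with an exact conditional 95% interval in place of the Wald interval, together with the rate difference per 100 patient-years. Name Clopper-Pearson or mid-P beforehand, since they differ (2.43 against 1.85 in the example).

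The cost is one sentence and standard software options. The exact interval carries none of the Table 8-3 covariates and may be somewhat wider than Wald when both exist. It also treats events as independent, so the number of patients with an event should be shown beside the event count.
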